7.3. Lost to Follow up

A participant will be considered lost to follow-up if he or she repeatedly fails to return for scheduled visits and is unable to be contacted by the study site. Site personnel or designee are expected to make diligent attempts to contact participants who fail to return for a scheduled visit or were otherwise unable to be followed up by the site.

8. Study Assessments and Procedures

Study procedures and their timing are summarized in the SoA.

Immediate safety concerns should be discussed with the sponsor immediately upon occurrence or awareness to determine if the participant should continue or discontinue study intervention.

Adherence to the study design requirements, including those specified in the SoA, is essential and required for study conduct.

All screening evaluations must be completed and reviewed to confirm that potential participants meet all eligibility criteria. The investigator will maintain a screening log to record details of all participants screened and to confirm eligibility or record reasons for screening failure, as applicable.

8.1. Efficacy Assessments

Efficacy will be measured by

- HbA1c
- time in range between 70 and 180 mg/dL (3.9 and 10.0 mmol/L), inclusive, and
- patient-reported outcomes questionnaires
 - Diabetes Treatment Satisfaction Questionnaire - Status
 - Diabetes Treatment Satisfaction Questionnaire - Change
 - SF-36v2 acute form
 - EQ-5D-5L
 - Basal Insulin Experience: Preference, and
 - Basal Insulin Experience: Likelihood of incorporating into routine.

See Section 3 for specific efficacy endpoints.

This section will outline glucose monitoring and patient-reported outcome measures.

8.1.1. Glucose Monitoring

Participants **must** use only the study-provided glucose monitors during the study.

8.1.1.1. Self-Monitoring of Blood Glucose (SMBG)

Glucometer for participant use during the study

Participants will receive a study-approved glucometer and related testing supplies for use during the study.

Site personnel will train the participant on correct use of the glucometer for self-monitoring blood glucose and reporting of hypoglycemia data in the e-diary.

Fasting blood glucose (FBG) measurement

The FBG should be measured upon waking in the morning, prior to food or caloric beverage intake.

This table describes when participants will measure their FBG using the study-provided glucometer.

The participant must measure their FBG during...	At a frequency of...
Weeks -1 to 0 Visits 2 to 3	
Weeks 0 to 12 Visits 3 to 15	3 days per week
the week prior to Weeks 16, 20, 24, 26, 28, 32, 36, 40, 44, 48, and 52 Visits 17, 19, 21, 22, 23, 24, 25, 26, 27, 28, and 29	

Additional FBG and SMBG measurements can be obtained as clinically indicated.

SMBG for suspected hypoglycemia

Participants will be advised to check SMBG readings when they experience signs and symptoms of hypoglycemia and for CGM glucose < 70 mg/dL (3.9 mmol/L) prior to treatment with carbohydrates (if the participants can safely do this).

The participant's SMBG readings and hypoglycemia events in conjunction with CGM data will be used to determine insulin dosing during the study (Section 6.5).

Glucometer data transfer

The study-provided glucometer will wirelessly transmit blood glucose measurements to the participant's e-diary. Site personnel will be able to view SMBG data that have been transmitted to the e-diary through a web-based portal as well as any reported events of hypoglycemia.

8.1.1.2. Continuous Glucose Monitoring (CGM) System

The unblinded Dexcom G6® CGM system will be used continuously throughout the study to facilitate diabetes management and for data collection. The Dexcom G6 CGM system includes the sensor, transmitter, and receiver.

Training and initiation

At Visit 2, participants will receive the study supplied CGM system and training on its use and study requirements. The sensor can be worn for up to 10 days. Participants will be instructed to change the sensor and transmitter before they expire according to the product label information and to keep the transmitter within 20 feet (6 meters) of the receiver during use. Study participants will use the receiver to review CGM data during the study. A CGM participant user

guide that provides an overview of device components and study-specific instructions will be available for at-home use.

Site personnel will download the CGM data from the receiver to a vendor online portal where data can be reviewed as per the SoA and as clinically indicated.

Notes:

- Participants are not allowed to connect the transmitter of the study supplied Dexcom G6 system to a personal smartphone, smartphone application, or other system.
- The sensor code must be entered into the CGM receiver. Participants are not allowed to manually calibrate the study CGM with fingerstick blood glucose readings.
- Participants may not use their own personal CGM device.

In the CGM receiver, a hypoglycemia alert at 70 mg/dL (3.9 mmol/L) will be required.

Participants will be advised to check SMBG readings when they experience signs and symptoms of hypoglycemia and for CGM glucose <70 mg/dL (3.9 mmol/L) prior to treatment with carbohydrates (if the participant can safely do this).

CGM data compliance

Sites will be required to review data capture compliance following CGM data downloads using the available vendor portal reports and visualization tools. A compliance threshold of 80% will be used to assess minimum CGM data capture requirements are met and is defined as the percentage of actual data versus expected data collected in between data downloads. Site personnel will re-educate participants on CGM requirements when download compliance is <80%.

To minimize data loss, the CGM service vendor will review site downloads and notify site users when sessions do not meet the compliance threshold. CGM compliance reports will also be provided to the sponsor and site monitors during the study for review and to determine if further mitigation is necessary.

8.1.2. Patient-Reported Outcomes

The self-administered questionnaires will be translated into the native language of the region and administered at the site during the designated visits in the SoA (Section 1.3).

Order of administering the questionnaires during the visit

The questionnaires should be completed before the participant has discussed their medical condition or progress in the study with the investigator or study personnel, if the participant is not adversely affected by their fasting condition.

The order of administration of these questionnaires, where applicable, is

- Diabetes Treatment Satisfaction Questionnaire - Status
- Diabetes Treatment Satisfaction Questionnaire - Change
- SF-36v2 acute form
- EQ-5D-5L
- Basal Insulin Experience: Preference, and
- Basal Insulin Experience: Likelihood of incorporating into routine.

8.1.2.1. Diabetes Treatment Satisfaction Questionnaire – Status

The Diabetes Treatment Satisfaction Questionnaire-Status Version (Bradley and Lewis 1990; Bradley 1994) is a diabetes-specific patient-reported outcome instrument that assesses the overall treatment satisfaction and perceived frequency of hyperglycemia and hypoglycemia. It is appropriate for use in both T1D and T2D.

The Diabetes Treatment Satisfaction Questionnaire-Status Version consists of 8 items that assess treatment satisfaction as well as concerns about hyperglycemia and hypoglycemia over the past few weeks, prior to the visit.

Each item is rated on a 7-point Likert scale. Items 1, 4, 5 to 7, and 8 are rated from 0 (very dissatisfied) to 6 (very satisfied) and can be summed up to produce a treatment satisfaction score. Items 2 and 3 evaluate the perceived frequency of hyperglycemia and hypoglycemia and are rated from 0 (none of the time) to 6 (most of the time).

8.1.2.2. Diabetes Treatment Satisfaction Questionnaire – Change

The Diabetes Treatment Satisfaction Questionnaire-Change Version (Bradley 1999) was designed to overcome potential ceiling effects in the status version. The Diabetes Treatment Satisfaction Questionnaire-Change Version has the same 8 items as the status version but is reworded slightly to measure the change in treatment satisfaction rather than absolute treatment satisfaction.

Each item is scored on a scale of -3 to +3. For all items except Item 2 (perceived frequency of hyperglycemia) and Item 3 (perceived frequency of hypoglycemia):

- the higher the score, the greater the improvement in treatment satisfaction
- the lower the score, the greater the deterioration in treatment satisfaction, and
- a score of 0 represents no change.

For Items 2 and 3: the lower the score, the better the perception.

8.1.2.3. Short Form-36 Version 2 Health Survey Acute Form

Description of SF-36v2

The SF-36 v2 Health Survey Acute form is a participant self-administered measure designed to assess these 8 domains

- Physical Functioning
- Role Physical
- Bodily Pain
- General Health
- Vitality
- Social Functioning
- Role Emotional, and
- Mental Health.

The Physical Functioning domain assesses limitations due to health “now” while the remaining domains assess functioning “in the past week.” Participants answer each item using Likert 3-point, 5-point, or 6-point scales for the responses.

Scoring

Each domain is scored individually and information from these 8 domains is further aggregated into 2 health component summary scores, the Physical Component Summary and Mental Component Summary.

Scoring of each domain and both summary scores are norm based and presented in the form of T-scores, with a mean of 50 and standard deviation of 10.

Higher scores indicate better levels of function and/or better health (Maruish 2011).

8.1.2.4. EQ-5D-5L

Description of EQ-5D-5L

The EQ-5D-5L (EuroQol Research Foundation 2019) is a standardized, 5-item, self-administered instrument for use as a measure of health outcome. It provides a simple, descriptive health profile and a single health state index value that can be used in the clinical and economic evaluation of health care as well as population health surveys.

The EQ-5D-5L assesses 5 dimensions of health

- mobility
- self-care
- usual activities
- pain/discomfort, and
- anxiety/depression.

The 5L version scores each dimension at 5 levels

- no problems
- slight problems
- moderate problems
- severe problems, and
- unable to perform/extreme problems.

A total of 3125 health states is possible.

Scoring

The scores on the 5 dimensions can be presented as a health profile or converted to a single health state index value.

The single health state index value can be derived based on a formula that attaches weights to each of the levels in each dimension. This index value ranges between less than 0 to 1, where negative values are valued as worse than dead, 0 is a health state equivalent to death, and 1 represents perfect health.

EQ Visual Analog Scale

The EQ Visual Analog Scale records the respondent's self-rated health status on a vertical graduated visual analog scale from 0 to 100, where 0 represents the worst imaginable health and 100 represents the best imaginable health.

In conjunction with the health state data, this provides a composite picture of the respondent's health status.

8.1.2.5. Basal Insulin Experience: Preference

The Basal Insulin Experience: preference is a self-report scale consisting of a single question to understand the participant's preference for their pre-study or current study treatment.

The question is rated on a 5-point scale with responses ranging from "strongly prefer the study insulin" to "strongly prefer my previous insulin." The question also includes a "not applicable" option for participants that stayed on the same insulin in the treatment phase.

8.1.2.6. Basal Insulin Experience: Likelihood of Incorporating into Routine

Description of questionnaire

The Basal Insulin Experience: Likelihood of incorporating into routine is a self-reported scale consisting of a single question to understand the participant's likelihood of incorporating their study insulin into their diabetes management routine.

Scoring

The question is rated on a 5-point scale with responses ranging from "very unlikely" to "very likely."

8.2. Safety Assessments

Planned time points for all safety assessments are provided in the SoA.

8.2.1. Physical Examinations

Physical examination at screening

The complete physical examination will include, at a minimum, assessments of these systems

- cardiovascular
- respiratory
- gastrointestinal, and
- neurologic.

Height and weight will be measured and recorded.

Additional assessments include clinical signs and symptoms related to T1D, T1D-related illnesses, and injection site reactions.

8.2.2. Vital Signs

Blood pressure and pulse rate will be measured when specified in the SoA and as clinically indicated. Additional vital signs may be measured during study visits if warranted, as determined by the investigator.

8.2.3. *Electrocardiograms*

Local and single 12-lead ECG will be obtained as outlined in the SoA.

Electrocardiograms will initially be interpreted by the investigator or qualified designee at the site as soon after the time of ECG collection as possible, and ideally while the participant is still present, to determine whether the participant meets entry criteria and for immediate participant management, should any clinically relevant findings be identified.

The investigator or qualified designee is responsible for determining if any change in participant management is needed and must document their review of the ECG printed at the time of evaluation.

8.2.4. *Clinical Safety Laboratory Tests*

See Section [10.2](#) for the list of clinical laboratory tests to be performed and the SoA for the timing and frequency.

The investigator must review the laboratory results, document this review, and report any clinically relevant changes occurring during the study as an AE.

The laboratory results must be retained with source documents unless a Source Document Agreement or comparable document cites an electronic location that accommodates the expected retention duration.

Clinically significant abnormal laboratory findings are those which are not associated with the underlying disease, unless judged by the investigator to be more severe than expected for the participant's condition.

All laboratory tests with values considered clinically significantly abnormal during participation in the study or within 5 weeks after the last dose of intervention should be repeated until the values return to normal or baseline or are no longer considered clinically significant by the investigator or medical monitor.

If such values do not return to normal/baseline within a period of time judged reasonable by the investigator, the etiology should be identified, and the sponsor notified.

All protocol-required laboratory assessments, as defined in Section [10.2](#), must be conducted in accordance with the SoA, standard collection requirements, and laboratory manual.

If laboratory values from non-protocol specified laboratory assessments performed at an investigator-designated local laboratory require a change in participant management or are considered clinically significant by the investigator (for example, SAE or AE or dose modification), then report the information as an AE.

8.2.5. Hepatic Monitoring

Close hepatic monitoring

Initiating laboratory and clinical monitoring for abnormal liver laboratory test results

Laboratory tests, including ALT, AST, ALP, TBL, direct bilirubin, GGT, and creatine kinase, should be repeated within 48 to 72 hours to confirm the abnormality and to determine if it is increasing or decreasing, if 1 or more of these conditions occur. This table shows when to repeat laboratory tests.

If a participant with baseline results of...	develops the following elevations:
ALT or AST <1.5x ULN	ALT or AST \geq 3x ULN
ALP <1.5x ULN	ALP \geq 2x ULN
TBL <1.5x ULN	TBL \geq 2x ULN (except for participants with Gilbert's syndrome)
ALT or AST \geq 1.5x ULN	ALT or AST \geq 2x baseline
ALP \geq 1.5x ULN	ALP \geq 2x baseline
TBL \geq 1.5x ULN	TBL \geq 1.5x baseline (except for participants with Gilbert's syndrome)

What to do if the abnormal condition persists or worsens

If the abnormal liver test result persists or worsens, clinical and laboratory monitoring, and evaluation for possible causes of abnormal liver tests should be initiated by the investigator in consultation with the Lilly-designated medical monitor. At a minimum, this evaluation should include physical examination and a thorough medical history, including

1. symptoms
2. recent illnesses, for example, heart failure, systemic infection, hypotension, or seizures
3. recent travel
4. history of concomitant medications, including over-the-counter, herbal and dietary supplements, and
5. history of alcohol drinking and other substance abuse.

Frequency of monitoring

Initially, monitoring of symptoms and liver tests should be done 1 to 3 times weekly, based on the participant's clinical condition and liver test results.

Subsequently, the frequency of monitoring may be lowered to once every 1 to 2 weeks, if the participant's clinical condition and laboratory results stabilize.

Monitoring of ALT, AST, ALP, and TBL should continue until levels normalize or return to approximate baseline levels.

Comprehensive hepatic evaluation

When to perform a comprehensive evaluation

A comprehensive evaluation should be performed to search for possible causes of liver injury if 1 or more of the conditions in this table occur.

If a participant with baseline results of...	develops the following elevations:
ALT or AST <1.5x ULN	ALT or AST \geq 3x ULN with hepatic signs or symptoms ^a , or ALT or AST \geq 5x ULN
ALP <1.5x ULN	ALP \geq 3x ULN
TBL <1.5x ULN	TBL \geq 2x ULN (except for participants with Gilbert's syndrome)
ALT or AST \geq 1.5x ULN	ALT or AST \geq 2x baseline with hepatic signs or symptoms ^a , or ALT or AST \geq 3x baseline
ALP \geq 1.5x ULN	ALP \geq 2x baseline
TBL \geq 1.5x ULN	TBL \geq 2x baseline (except for participants with Gilbert's syndrome)

^a Hepatic signs or symptoms are severe fatigue, nausea, vomiting, right upper quadrant abdominal pain, fever, rash, and/or eosinophilia >5%.

What a comprehensive evaluation should include

At a minimum, this evaluation should include

- physical examination and a thorough medical history, as outlined above
- tests for
 - PT-INR
 - viral hepatitis A, B, C, or E, and
 - autoimmune hepatitis, and
- an abdominal imaging study, for example, ultrasound or computed tomography scan.

Based on the patient's history and initial results, further testing should be considered in consultation with the Lilly-designated medical monitor, including tests for

- hepatitis D virus
- cytomegalovirus
- Epstein-Barr virus
- acetaminophen levels
- acetaminophen protein adducts
- urine toxicology screen
- Wilson's disease
- blood alcohol levels
- urinary ethyl glucuronide, and
- blood phosphatidylethanol.

Based on the circumstances and the investigator's assessment of the participant's clinical condition, the investigator should consider referring the participant for a hepatologist or gastroenterologist consultation, magnetic resonance cholangiopancreatography, endoscopic retrograde cholangiopancreatography, cardiac echocardiogram, or a liver biopsy.

Additional hepatic data collection (hepatic safety CRF) in study participants who have abnormal liver tests during the study

Collect additional hepatic safety data collection in the hepatic safety CRFs if a participant

- develops a hepatic event considered to be an SAE, or
- discontinues study intervention due to a hepatic event, or
- has changes in laboratory results described in this table.

If a participant with baseline results of...	develops the following elevations...	Then...
Elevated serum ALT		
ALT <1.5x ULN	ALT to ≥ 5 x ULN on 2 or more consecutive blood tests	Collect additional hepatic safety data in the hepatic safety CRF.
ALT ≥ 1.5 x ULN	ALT ≥ 3 x baseline on 2 or more consecutive blood tests	
Elevated TBL		
TBL <1.5x ULN	TBL ≥ 2 x ULN (except for participants with Gilbert's syndrome)	Collect additional hepatic safety data in the hepatic safety CRF.
TBL ≥ 1.5 x ULN	TBL ≥ 2 x baseline	
Elevated ALP		
ALP <1.5x ULN	ALP ≥ 2 x ULN on 2 or more consecutive blood tests	Collect additional hepatic safety data in the hepatic safety CRF.
ALP ≥ 1.5 x ULN	ALP to ≥ 2 x baseline on 2 or more consecutive blood tests	

Note: The interval between the 2 consecutive blood tests should be at least 2 days.

See Section 10.5 for hepatic laboratory tests.

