5.2. Exclusion Criteria

Participants are excluded from the study if any of the following criteria apply:

Medical conditions***Diabetes related***

9. Have a diagnosis of T2D, latent autoimmune diabetes, or specific types of diabetes other than T1D, for example, monogenic diabetes, diseases of the exocrine pancreas, and drug-induced or chemical-induced diabetes.
10. Have a history of more than 1 episode of severe hypoglycemia, defined as requiring assistance due to neurologically disabling hypoglycemia, within the 6 months prior to screening.
11. Have hypoglycemia unawareness, in the opinion of the investigator.
12. Have a history of more than 1 episode of diabetic ketoacidosis or hyperosmolar state or coma requiring hospitalization within the 6 months prior to screening.
13. Have excessive insulin resistance, defined as having received a total daily dose of insulin >1.5 units/kg at the time of screening.

Cardiovascular

14. Have had New York Heart Association Class IV heart failure or any of the following cardiovascular conditions within 90 days prior to screening
 - acute myocardial infarction
 - cerebrovascular accident (stroke), or
 - coronary bypass surgery.

Gastrointestinal

15. Have undergone gastric bypass (bariatric) surgery, restrictive bariatric surgery, for example, Lap-Band[®] or sleeve gastrectomy within 1 year prior to screening.
16. Have presence of clinically significant gastroparesis, in the opinion of the investigator.

Hepatic

17. Have acute or chronic hepatitis, cirrhosis, or obvious clinical signs or symptoms of any other liver disease, except nonalcoholic fatty liver disease (that is, study participants with nonalcoholic fatty liver disease are eligible for participation), or have elevated liver enzyme measurements as determined by the central laboratory at screening:
 - total bilirubin >2x ULN except for participants with Gilbert's syndrome
 - ALT or serum glutamic pyruvic transaminase >3x ULN
 - AST or serum glutamic oxaloacetic transaminase >3x ULN, or
 - ALP >2.5x ULN.

Renal

18. Have a history of renal transplantation, are currently receiving renal dialysis, or have an estimated glomerular filtration rate <30 mL/min/1.73 m², calculated by the Chronic Kidney Disease-Epidemiology equation, as determined by the central laboratory at screening.

Hematologic

19. Have had a blood transfusion or severe blood loss within 90 days prior to screening.

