7.1.1. Liver Chemistry Stopping Criteria

The study intervention should be interrupted or discontinued if 1 or more of these conditions occur.

Elevation	Exception
ALT or AST >8x ULN	
ALT or AST >5x ULN for more than 2 weeks	
ALT or AST >3x ULN and either TBL >2x ULN or INR >1.5	In participants with Gilbert's syndrome, doubling of direct bilirubin should be used for intervention interruption or discontinuation decisions rather than TBL >2x ULN.
ALT or AST >3x ULN with the appearance of fatigue, nausea, vomiting, right upper quadrant pain or tenderness, fever, rash, and/or eosinophilia (>5%)	
ALP >3x ULN, when the source of increased ALP is the liver	
ALP >2.5x ULN and TBL > 2x ULN	In participants with Gilbert's syndrome, doubling of direct bilirubin should be used for intervention interruption or discontinuation decisions rather than TBL >2x ULN.

ALP >2.5x ULN with the appearance of fatigue, nausea, vomiting, right upper quadrant pain or tenderness, fever, rash, and/or eosinophilia (>5%)	
---	--

Resumption of the study intervention can be considered only in consultation with the Lilly-designated medical monitor and only if the liver test results return to baseline and if a self-limited, non-intervention etiology is identified.

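### PT-INR is one limb of a liver stopping rule from ALT or AST >3x ULN, but with no symptoms and normal-range triggers the protocol does not call for it until 5x ULN (baseline ALT/AST <1.5x ULN) or 3x baseline (baseline at or above 1.5x ULN)

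*Protocol*

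**What the plan says.** Protocol Section 7.1.1 lists conditions any one of which should lead to interruption or discontinuation. Those that turn on ALT or AST are:

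- above 8x ULN;
- "ALT or AST >5x ULN for more than 2 weeks";
- "ALT or AST >3x ULN and either TBL >2x ULN or INR >1.5";
- above 3x ULN with a listed sign or symptom. That list includes fatigue, without a grade.

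Section 8.2.5 then sets out which tests follow an abnormal result, in steps.

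- **Repeat.** "Laboratory tests, including ALT, AST, ALP, TBL, direct bilirubin, GGT, and creatine kinase, should be repeated within 48 to 72 hours". ALT or AST triggers this at 3x ULN if baseline is below 1.5x ULN, otherwise at 2x baseline.
- **Persisting or worsening result.** Clinical and laboratory monitoring and a search for causes, in consultation with the medical monitor. The stated minimum is a physical examination and a history.
- **Frequency.** "Initially, monitoring of symptoms and liver tests should be done 1 to 3 times weekly"; later "the frequency of monitoring may be lowered to once every 1 to 2 weeks".
- **Duration.** "Monitoring of ALT, AST, ALP, and TBL should continue until levels normalize or return to approximate baseline levels".
- **Comprehensive evaluation.** This is the only step that names PT-INR. ALT or AST alone triggers it at 5x ULN (baseline below 1.5x ULN) or 3x baseline. With signs or symptoms the thresholds fall to 3x ULN or 2x baseline. The footnote defines these: "Hepatic signs or symptoms are severe fatigue, nausea, vomiting, right upper quadrant abdominal pain, fever, rash, and/or eosinophilia >5"%.

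The Schedule of Activities and Appendix 2 list no coagulation test. Appendix 5 lists PT-INR but refers back to Section 8.2.5 for the choice of tests. Exclusion criterion 17 allows ALT and AST up to 3x ULN at screening, and "study participants with nonalcoholic fatty liver disease are eligible for participation".

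**The concern.** The stopping rule and the testing steps start at different levels. The word joining bilirubin and INR in Section 7.1.1 is *or*, so a raised INR is enough without raised bilirubin. The rule can therefore be applied in full only if INR is known once ALT or AST passes 3x ULN. A site that carries out Section 8.2.5 exactly as written can reach the stop decision with that value unmeasured. Sites may also differ in whether they think to order it. At stake is consistent use of one participant-protection rule in a narrow band of liver enzyme values.

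**Working it through.** The documents give no figure to reproduce here. The check compares thresholds.

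**Inputs.** The INR limb starts at ALT or AST >3x ULN (Section 7.1.1). The thresholds for the repeat and for the comprehensive evaluation come from the Section 8.2.5 tables. Let *b* be baseline ALT or AST in multiples of ULN. Screening allows *b* up to 3.

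**Conditions.** Baseline TBL below 1.5x ULN, current TBL below 2x ULN, ALP below its triggers, and none of the signs or symptoms in Section 7.1.1.

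**Step 1: is another ALT/AST criterion already met?** Take *b* below 1.5 and a current value from >3x to <5x ULN. The >8x rule and the rule of >5x for more than 2 weeks do not apply. The symptom criterion and the bilirubin limb are excluded by the conditions. INR is the remaining limb of the >3x ULN criteria.

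**Step 2: does any step call for INR?** The repeat is triggered at 3x ULN but does not name INR. Neither does the minimum for a persisting result, nor the list for continued monitoring. The comprehensive evaluation starts at 5x ULN. So from >3x to <5x ULN no step calls for it.

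**Step 3: why the conditions are needed.** Without them the range includes cases where INR decides nothing.

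- *Bilirubin.* With baseline TBL at or above 1.5x ULN, the Section 8.2.5 triggers are 1.5x baseline (repeat) and 2x baseline (comprehensive evaluation). At a baseline TBL of 1.5x ULN these are 1.5 × 1.5 = 2.25x and 2 × 1.5 = 3x ULN. A TBL just above 2x ULN is below both, yet already meets the bilirubin limb.
- *Fatigue.* Section 7.1.1 counts any fatigue, while the Section 8.2.5 footnote requires severe fatigue. Non-severe fatigue with ALT or AST >3x ULN already meets a stopping criterion without triggering the comprehensive evaluation.

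**Step 4: higher baselines.** For *b* at or above 1.5, the ALT/AST trigger for PT-INR is now 3*b*. If PT-INR joins the repeat, it becomes 2*b*.

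| Baseline ALT/AST (x ULN) | Trigger now | PT-INR not called for now | Trigger after fix | Range left after fix |
|---|---|---|---|---|
| below 1.5 | 5 | >3x to <5x | 3 | none |
| 1.5 | 3 × 1.5 = 4.5 | >3x to <4.5x | 2 × 1.5 = 3 | none |
| 2 | 3 × 2 = 6 | >3x to <6x | 2 × 2 = 4 | >3x to <4x |
| 2.5 | 3 × 2.5 = 7.5 | >3x to <7.5x | 2 × 2.5 = 5 | >3x to <5x |
| 3 | 3 × 3 = 9 | >3x to <9x; INR matters only up to 8x | 2 × 3 = 6 | >3x to <6x |

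Above 8x ULN the separate rule already stops treatment. Above 5x ULN the rule for more than 2 weeks also runs. These are ranges on the ALT/AST scale, not shares of participants.

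**The case against.** The strongest reply is that the protocol already leaves a route to INR. The repeat list is open, since it begins with *including*. The step for a persisting result sets only a minimum and brings in the medical monitor. Section 8.2.5 points to the Appendix 5 test list, which contains PT-INR. Appendix 5 allows local testing for immediate management, and Appendix 2 allows additional tests at any time. Escalation by steps is also a reasonable design: symptoms are rechecked with the liver tests, and a qualifying symptom at 3x ULN or above brings in PT-INR for baseline ALT/AST below 1.5x ULN.

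Much of this stands. A reader might infer that the protocol rules INR out in this range, or that a liver injury would go unnoticed. The documents support neither. INR can be ordered. With baseline below 1.5x ULN the abnormality is repeated from 3x ULN and, if it persists, followed with the medical monitor. It would also go too far to say that INR always decides below the 5x trigger; the bilirubin and fatigue cases above show otherwise.

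What does not stand is the step from permitted to called for. The list names seven tests, including creatine kinase, but not the one that the stopping rule uses. Stepwise escalation explains deferring viral serology and imaging, which look for a cause. It does not explain deferring an input to a stop decision that applies from >3x ULN. The prothrombin time levels in SAP Appendix 10 (Section 6.10) do not fill the gap either: they classify results and do not require the test.

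**Conclusion.** The mismatch is real and narrow. In the main case it covers >3x to <5x ULN under the stated conditions. With baseline ALT/AST at or above 1.5x ULN it covers >3x ULN to <3x baseline, subject to the other ALT/AST stops.

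Three frequencies are missing from the documents: how often baselines reach 1.5x ULN, how often INR exceeds 1.5 in this setting, and how many participants would enter the range. Such baselines are assumed uncommon, because criterion 17 excludes most liver disease, though it does permit them. The other two are assumed small.

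This is a minor participant-safety correction. A reader might extend it to the trial's results, but the primary and key secondary endpoints, their estimands and the sample size do not depend on it.

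**What to change.** In Section 8.2.5:

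1. Add PT-INR to the 48 to 72 hour repeat when ALT or AST triggers it, not when ALP or TBL alone does.
2. Repeat PT-INR during monitoring if ALT or AST stays >3x ULN and is rising, or if the earlier INR was abnormal.

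The stopping criteria and all trigger thresholds stay as they are. This closes the range for baseline ALT/AST below 1.5x ULN. For baselines above 1.5x ULN a range from >3x ULN to <2x baseline remains, because the repeat trigger is unchanged. A further trigger at >3x ULN for these participants would close it, but near a baseline of 3x ULN it would fire on trivial fluctuation, so it is best left optional.

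The cost is wording in one section and one extra coagulation test on a draw that already takes place, plus repeats only where rule 2 applies. Appendix 5 already lists the test for the central laboratory. Testing at every monitoring draw is more than the gap needs. With assumed durations of 2 weeks at 1 to 3 draws per week (2 to 6) and 4 weeks at one draw per 1 to 2 weeks (2 to 4), plus 1 at the repeat, it would mean 5 to 11 tests per affected participant.
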